4.3 Background and Demographic Characteristics

4.3.1 Demography

Demographic characteristics (age, sex, ethnic origin and race), dominant arm, body measurements (height, weight and BMI), collected at baseline will be summarised.

Age is calculated in years from the date of [REDACTED] of active treatment.

Body mass index (BMI) is calculated as (weight (kg)/height (m)²).

All subject demographic data, also including informed consent, will be listed.

4.3.2 Medical/Surgical History

Medical/surgical history events will be coded using the latest MedDRA dictionary version. The number and percentage of subjects will be presented for ongoing conditions and previous conditions separately by SOC, and PT, where SOC and PT will be presented in decreasing frequency of the total number of subjects with medical history events. All events will be listed, which will include a flag for ongoing and previous conditions.

4.3.3 Myotonic Dystrophy Diagnosis

Myotonic dystrophy diagnosis (congenital or juvenile-onset) and the congenital and juvenile-onset signs and symptoms will be summarised. Baseline signs and symptoms will be summarised by SOC and PT and by SOC, PT and severity.

Myotonic dystrophy diagnosis information and baseline signs data will be listed.

4.4 Administration of Investigational Product

Percentage compliance with administration of active treatment will be summarised (see section 4.2 for the derivation).

The following active treatment exposure summaries will also be provided: total amount (mg) of active treatment taken (see section 4.2 for derivation) and the number of days of exposure to the active treatment derived from the subject diary card data as follows:

(Date of [REDACTED] of [REDACTED] of active treatment – date of [REDACTED] of [REDACTED] of active treatment + 1) + (Date of [REDACTED] of [REDACTED] of active treatment – date of [REDACTED] of [REDACTED] of active treatment + 1), where the [REDACTED] duration is only applicable to subjects who are [REDACTED]

In addition, the following active treatment exposure summaries will be provided for Cohort 1 subjects:

- the number of days of exposure to [REDACTED] tideglusib for all Cohort 1 subjects and separately for Cohort 1 subjects who are [REDACTED] from [REDACTED] tideglusib defined as:

Date of [REDACTED] of [REDACTED] of active treatment – date of [REDACTED] of [REDACTED] of active treatment + 1.

- the number of days of exposure to [REDACTED] tideglusib for subjects who are [REDACTED] from [REDACTED] tideglusib defined as:

Date of [REDACTED] of [REDACTED] of active treatment – date of [REDACTED] of [REDACTED] of active treatment + 1.

- the number of subjects that were [REDACTED]

[REDACTED] dose, the additional variables outlined above for Cohort 1 will be derived for both Cohorts.

The above derived variables and study drug dispensing, study drug return, study drug down titration and subject diary card information will be listed.

5 EFFICACY EVALUATION

5.1 Efficacy Endpoints

The efficacy endpoints have been grouped into 4 efficacy endpoint “families” detailed in sections 5.1.1 to 5.1.4 below.

In addition to the analyses detailed in these sections, score card values [REDACTED] will be derived for each subject based on the [REDACTED] given in Table 1 below, where any endpoint not meeting the criteria will be assigned a score of [REDACTED].

Score card values will be derived for each subject at each of [REDACTED] and [REDACTED]. Where an endpoint is not scheduled to be collected at the respective visit, a score will not be derived and N/A will be displayed in the listing. Where an endpoint is scheduled to be collected but is missing, the score will be displayed as ND.

At [REDACTED] only, a total score card value will be calculated for each subject as the sum of the [REDACTED]. If any endpoint score is missing at these scheduled visits, the total score will not be calculated for the respective visit and subject. The scorecard values for each of the [REDACTED] detailed in Table 1 and the total score card value will be listed by Visit for each subject.

Mean total scores at [REDACTED] will be calculated by dose group and compared using a t-test. Additionally, the [REDACTED] total scores will be compared between the two dose groups using a Wilcoxon rank-sum test. Summary statistics will be presented for the dose group total scores at [REDACTED] together with the p-values from the comparisons between

dose groups. Since this is a non-randomised trial, there will be a known potential for any comparison of dose groups to be biased. This will be addressed via examination of the by cohort summary statistics for baseline characteristics and baseline efficacy measurements. If it is determined that there are large differences between cohort characteristics at baseline, further exploratory analysis may be performed for the comparison of total scores with adjustment for baseline characteristics.

Table 2:

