19. Clinical history of hepatitis, previous or current positive serological evidence for hepatitis B or C
20. Serological evidence of Hepatitis A at [REDACTED] or in the [REDACTED] preceding [REDACTED]
21. A history of significant drug allergy (such as Steven-Johnson syndrome, anaphylaxis)
22. A history of alcohol or substance use disorders
23. Current malignancy or any history of malignancy except for surgically-cured skin cancer or pilomatricoma (benign tumour of the hair follicle that is associated with DM-1).
24. Severe arthritis or other medical condition (besides DM-1) that would significantly impact ambulation
25. Use within 4 weeks prior to [REDACTED] of strong CYP3A4 inhibitors e.g. clarithromycin, telithromycin, ketoconazole, itarconazole, posaconazole, nefazadone, indinavir, ritonavir
26. Concurrent use of drugs metabolised by CYP3A4 with a narrow therapeutic window e.g. warfarin and digitoxin
27. Judged clinically to be at risk of suicide (suicidal ideation, severe depression, or other factors) over the last three months, as assessed by the Investigator.
28. Hypersensitivity to tideglusib or any components of its formulation including allergy to strawberry
29. BMI of less than 14.0 kg/m^2 or greater than 40.0 kg/m^2 at [REDACTED]

\* Acceptable contraception is considered to be using one of the following birth control methods and should be in place for the duration of the study and for 30 or 90 days after last dose of IMP, respectively for female and male subjects:

- Surgical sterilisation of either the female subject in study (e.g., bilateral tubal ligation) or of her male partner (vasectomy with documented azoospermia) if he is the sole partner of that subject
- Established hormonal contraception (implantable, patch, oral or intramuscular [IM]) administered for at least one month prior to study medication administration
- An intrauterine device (IUD) or intrauterine system (IUS) with failure rate of less than 1% per year inserted by qualified physician at least one month prior to study medication administration

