### 8.3 Study design

This is a single-blind, [ ] week study in adolescent and adult subjects with congenital or juvenile onset type 1 myotonic dystrophy (DM-1).

Approximately 16 subjects in total are planned to be enrolled and receive active IMP.

Participation for individual subjects will consist of an initial Screening of up to [ ] weeks (minimum of [ ] week) followed by a [ ] treatment phase. After this, subjects in Cohort 1 will be treated [ ] once daily orally for 12 weeks and Cohort 2 will be treated [ ] once daily orally for 12 weeks.

Once [ ] out of the [ ] subjects from Cohort 1, who have received active treatment with 1000mg of tideglusib, have completed or discontinued from the study ([ ]), the DSMC will meet to review the available data and a recommendation will be made to the Sponsor whether Cohort 2 should be initiated.

[ ] . No screening will take place for Cohort 2 until after the recommendation has been made from the DSMC, to the Sponsor, on if Cohort 2 should be initiated.

The study will have 4 distinct phases:

- Screening (weeks [ ] )

Informed consent and assent (as applicable – see section 13.3) must be performed before any protocol procedures are carried out. Subjects will be screened to ensure adherence to eligibility criteria. This must be performed at least 1 week prior to Run-in ([ ]). Laboratory tests may be repeated once during the screening window if laboratory exclusion criteria are met.

- [ ] run in (weeks [ ]) )

Subjects and their caregiver will be dispensed [ ] provided with instructions on when and how to administer the medication. Subject diaries will be dispensed to record the date and time of dose, any issue with taking the dose, information on the subject's [ ] status, time of first meal after dosing and the type of food eaten. These will be reviewed by the investigator site at each visit.

- Single-blind treatment with tideglusib 1000mg (N = 8) (Cohort 1) or 400mg (N = 8) (Cohort 2) for 12 weeks (weeks 0 to 12)

In cohort 1, the first 3 subjects will be dosed sequentially. The safety Week █ (█) laboratory data of the previous subject will be reviewed by the investigator and the medical monitor before the next subject will be dosed. The first 3 subjects will all be  $\geq 18$  years old.

After the review of laboratory results obtained at Week █ █ for the third subject, the remaining subjects in Cohort 1 can be dosed, including subjects of  $\geq 12$  to  $\leq 17$  years.

[figure not shown]

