Subjects will attend clinic for visits every █ weeks where diaries will be collected and accountability checked before dispensing additional IMP. Safety, efficacy and pharmacokinetic assessments will be performed according to the schedule of assessments.

Cohort 2 can begin after data collected in Cohort 1 (█)

█ (█) has been reviewed by the DSMC. Cohort 2 subjects will be treated as above with 400mg dose, however there will be no initial restriction on enrolment.

- Follow-up visit █ after end-of-treatment (weeks █)

The follow-up visit will take place in clinic, approximately █ after the EOT visit. Safety and efficacy assessments will be performed in line with the schedule of assessments.

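### The SAP's only explicit between-dose test is unadjusted, and adjustment for baseline differences is left to an undefined look at the data although the entry rules make an age imbalance expected

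*SAP*

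**What the plan says.** SAP 5.1 derives a total score card value for each subject. Mean totals "will be calculated by dose group and compared using a t-test", and "total scores will be compared between the two dose groups using a Wilcoxon rank-sum test". Neither test has a covariate, and both p-values are to be presented.

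The same paragraph concedes: "Since this is a non-randomised trial, there will be a known potential for any comparison of dose groups to be biased". Its answer is to inspect baseline summaries by cohort. Then: "If it is determined that there are large differences between cohort characteristics at baseline, further exploratory analysis may be performed", meaning a comparison of totals adjusted for baseline characteristics. It does not say what counts as large, who decides, which characteristics enter, or what model is used.

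Four other places bear on this:

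- Protocol section 11 says the statistical methods will take account of known potential confounders and gives baseline characteristics as an example. SAP 2.5 lists one departure from the protocol analyses, for a biomarker, and says there are no others.
- Protocol 9.3 allocates subjects to Cohort 1 and then Cohort 2 in sequence.
- Protocol 7.2 sets the same age range, 12 to 45 years, for both cohorts. For Cohort 1, Protocol 8.3 adds "The first 3 subjects will all be" at least 18. For Cohort 2, "there will be no initial restriction on enrolment".
- The MMRM and ANCOVA models in SAP 5.1.1 to 5.1.4 carry a dose-group term. Those fitted to change also adjust for the endpoint's own baseline value. Their listed outputs are least-squares means for each dose group with p-values. No dose-difference contrast is listed, and neither age nor weight is a covariate.

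**The concern.** Inspecting a baseline table can reveal a bias but does not remove it. The plan names a likely problem, then leaves the correction optional, exploratory and conditional on a judgement made after the data are in hand. Two analysts could look at the same 8 v 8 table and reasonably disagree about whether an adjusted result is called for, and then about which covariates to use.

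The age rule makes the issue more than hypothetical, because it pushes the cohorts apart in a known direction before anyone is enrolled. If the total score depends on age, part of any dose difference is an age difference. The between-dose p-values would still be reported, with no planned estimate that separates the two.

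**Working it through.** **The plan's own figure.** There is none to reproduce beyond 8 + 8 = 16. SAP 2.4 says no formal sample size calculation was done.

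**Inputs from the documents.** 8 subjects per cohort (SAP 2.4); 3 of the 8 in Cohort 1 must be adults (Protocol 8.3); two-sided tests (Protocol section 11), with 0.05 taken from the 95% intervals.

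**Assumed inputs.** The documents give neither the adolescent share nor the effect of age on the score. Let p be the probability that a freely enrolled subject is an adolescent (0.3 or 0.5), and b the adolescent-adult difference in total score in residual SD (0.5, 1 or 2). There is no true dose effect.

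**Step 1: imbalance built in by the entry rule.** Expected adolescents are 5p in Cohort 1 and 8p in Cohort 2. The gap in proportion is p − 5p/8 = 3p/8.

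- p = 0.3: 1.5 v 2.4 of 8, gap 0.1125
- p = 0.5: 2.5 v 4.0 of 8, gap 0.1875

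**Step 2: bias in the unadjusted difference.** Size of bias = (3p/8) × b. The smallest case is 0.1125 × 0.5 = 0.056 SD and the largest is 0.1875 × 2 = 0.375 SD. The direction depends on the sign of the age effect, which is unknown.

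**Step 3: false-positive rates, by simulation.** The adjusted model is a linear model with dose group and age class.

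| p | b | Size of simulated bias, unadjusted (SD) | t-test | Wilcoxon | Adjusted model | Bias, adjusted (SD) |
|---|---|---|---|---|---|---|
| 0.3 | 0.5 | 0.057 | 5.27% | 5.60% | 5.45% | −0.008 |
| 0.3 | 1 | 0.110 | 5.14% | 5.75% | 5.10% | 0.013 |
| 0.3 | 2 | 0.219 | 5.75% | 6.02% | 4.73% | 0.011 |
| 0.5 | 0.5 | 0.096 | 5.09% | 5.00% | 4.42% | −0.011 |
| 0.5 | 1 | 0.189 | 5.95% | 6.32% | 4.93% | 0.000 |
| 0.5 | 2 | 0.372 | 7.47% | 7.18% | 4.65% | 0.005 |

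The t-test column rests on 40,000 runs, the Wilcoxon on 4,000 and the adjusted model on up to 6,000. The Monte Carlo standard error near 5% is √(0.05 × 0.95/runs), or about 0.11, 0.34 and 0.28 percentage points. Departures from 5% in the b = 0.5 rows are within or close to that noise.

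**Step 4: precision, for scale.** With 14 degrees of freedom the observed difference must exceed 2.145 × √(2/8) = 1.07 within-cohort SD for p < 0.05. The largest bias above is at most about a third of that (0.37/1.07 = 0.35). SAP 5.1 gives no total when a component score is missing, so 14 is the maximum.

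**Limit of the check.** The adjusted model used the same adolescent/adult split that generated the data. A linear term in years would correct a stepwise age effect less exactly.

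**The case against.** The other side has a good case on several points.

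- **The SAP is open about the bias.** It promises the baseline tables, and the unadjusted p-values are presented in any event. A reader might infer that the analyst could swap an adjusted result for the raw one. The text does not support that: the adjusted analysis is an addition, so the discretion is over whether and how to add it.
- **Dose also appears elsewhere.** The MMRM and ANCOVA models contain a dose term, and F-tests are specified for the MMRMs. It would be wrong to say the doses are compared nowhere else or that nothing is baseline-adjusted. It remains true that the t-test and Wilcoxon are the only between-dose tests actually named.
- **The documented age rule is a weak force.** It touches 3 of 8 subjects, and in the weaker scenarios the false-positive rate is barely above 5%. This stands, and it limits the size of the point.
- **The score card criteria are redacted.** They may already score change from each subject's own baseline. Any age effect is therefore assumed. That argues equally for fixing the covariate before the totals are compared.
- **One covariate cannot repair a sequential, non-randomised design** in which site staff know the treatment (Protocol 9.3). Agreed; the adjusted result still needs that caveat.
- **The stakes are modest.** Safety is the primary objective, and no decision rule for these p-values is visible. If Cohort 2 were enrolled so that SAP 2.2 pools both cohorts as one dose group, the comparison would fall away.

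**Conclusion.** The point holds as a cheap improvement to the plan. The one explicit dose comparison ignores an age imbalance that the protocol itself creates, and the SAP's safeguard is optional and undefined, which sits badly with Protocol section 11. From the age rule alone, on the assumed inputs, the bias is about 0.06-0.37 SD and the t-test's false-positive rate about 5-7.5%. The top of that range needs half the free enrolments to be adolescents and an age effect of 2 SD. Sequential enrolment could produce larger differences, but the documents do not let them be sized.

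Three stronger readings are tempting and unsupported:

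- **False-positive rates of 11-15%.** These follow if the cohorts differ by 0.75-1 SD on a covariate correlated 0.5 with the score. Nothing in the documents points to an imbalance or correlation of that size.
- **Harm from chance imbalance.** With 8 per cohort the standardised difference has standard error √(2/8) = 0.5, so a gap above 0.5 SD on a given covariate arises by chance about 32% of the time. Chance imbalance does not raise the unconditional false-positive rate. It shows only that *large* needs a definition.
- **Confounding through overlapping mg/kg doses.** The documents give BMI limits but no heights, weights or mg/kg figures, so overlap rests on assumed body sizes. Even where present, it would blur the exposure contrast and would not in itself be baseline confounding.

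**What to change.** In SAP 5.1:

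1. Delete the conditional sentence about large baseline differences.
2. Pre-specify a linear model of total score on dose group plus age at first active dose, fitted whatever imbalance is observed. Report the adjusted dose difference with its 95% CI. Name this one covariate and leave no alternative open.
3. Show the t-test and Wilcoxon results beside it, labelled descriptive.
4. State that residual confounding remains because the cohorts were filled in sequence and without randomisation.

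No new data are needed; SAP 4.3.1 already derives and summarises age. The cost is one of 14 degrees of freedom, which raises the critical t value from 2.145 to 2.160, or 0.7%. There is also a small loss of precision if age is unrelated to the score or is correlated with cohort.

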5.1.1 Muscle Function

5.1.1.1 10 Metre Walk/Run Test

In the event that a subject does not complete a walk/run test, then that test result will not be included in derivation of the observed mean of the repeat assessments, which will use only "valid" results where the subject completed the assessment. A "valid" result will be any non-missing result where the recorded distance covered is not <10 metres. Where the distance is <10 metres, the test result will be assumed missing.

A MMRM will be fitted to the change from baseline to weeks █ and █ in the time taken (seconds) to complete the 10 metre walk/run test at the preferred speed (calculated for each visit as the mean of the repeat assessments). The model will include the baseline value as a covariate, dose group, and visit as fixed effects, and

the treatment-by-visit interaction. F-tests from PROC MIXED will be based on Kenward-Roger's adjusted degrees of freedom. A compound symmetry covariance matrix will be used for the repeated visits within subject.

Adjusted LS Means for the dose group means at each visit estimated by the above model will be presented, together with the associated SE, 95% CIs and 2-sided p-values.

The observed mean (of the repeat assessments at a visit) for the time taken (seconds) to complete the 10 metre walk/run test and the change from baseline will be summarised over time separately for the preferred speed and the fastest speed. The observed mean at the start of the [REDACTED] run-in [REDACTED] and at baseline (■) and the change from ■ to ■ in the observed mean will also be summarised separately for the preferred speed and the fastest speed.

The observed mean (of the repeat assessments at a visit) in the time taken (seconds) to complete the 10 metre walk/run test will be presented using by subject line plots over time (■, ■ ■ and ■) by dose group separately for the preferred speed and the fastest speed. In addition, line plots will present the adjusted LS mean changes from baseline and SEs over time, as estimated by the MMRM model, by dose group for the time taken (seconds) to complete the 10 metre walk/run test at the preferred speed. Raw mean changes from ■ to ■ will be presented on the same plot.

In order to assess the relationship between change from baseline to week ■ in the time taken to complete the 10 metre walk/run test at the preferred speed and the change from baseline to week ■ in total lean muscle mass, the change in the mean of the repeat assessments from baseline to week ■ in the time taken to complete the 10 metre walk/run test at the preferred speed will be plotted against the change from baseline to week ■ in total lean muscle mass.

The 10 metre walk/run test data will be listed.

5.1.1.2 Grip Strength and Muscle Relaxation Time

Grip strength and relaxation time are recorded in 2 separate trials for both the dominant and non-dominant hands, where in each trial there are 3 repeat assessments. For analysis purposes, the mean of the 2 trial results will be used, where for each trial the mean of the repeat assessments is taken.

A MMRM model will be fitted to the change from baseline to weeks [REDACTED] and ■ in the above derived mean per visit in the grip strength (kg) and separately for the muscle relaxation time (seconds) for the dominant hand. The model will include the baseline value as a covariate, dose group and visit as fixed effects, and the treatment-by-visit interaction. F-tests from PROC MIXED will be based on Kenward-Roger's adjusted degrees of freedom. The following variance/covariance matrix structures for the repeated visits within a subject will be assessed: Compound symmetry, 1st order autoregressive, Toeplitz and unstructured. The variance/covariance matrix structure that results in the smallest Akaike information criterion (AIC), indicating the best model fit will be selected.

The results from the above model will be presented as described in section 5.1.1.1.

The above derived mean grip strength and relaxation time and change from baseline will be summarised over time separately for the dominant and non-dominant hands. In addition, the observed mean at ■ and ■ and the change from ■ to ■ in the

observed mean will also be summarised separately for grip strength and relaxation time and for the dominant and non-dominant hands. The observed mean will also be presented using by subject line plots over time ([REDACTED] and [REDACTED]) by dose group separately for grip strength and relaxation time and for the dominant and non-dominant hands. In addition, line plots will present the adjusted LS mean changes from baseline and SEs over time, as estimated by the MMRM model, by dose group for grip strength and separately for the muscle relaxation time for the dominant hand. Raw mean changes from [REDACTED] to [REDACTED] will be presented on the same plot.

Grip strength and relaxation time data will be listed.

